Title:

Retrospective evaluation of clinical performance of the Astra Tech Implant System EV when used in everyday practice.

Identifier: NCT03845738

Document date: 20-Nov-2018

Retrospective evaluation of clinical performance of the Astra Tech Implant System EV when used in everyday practice.

Sponsor

DENTSPLY IH AB d.b.a. Dentsply Sirona Implants
[name]

(International) Coordinating Investigator

[name], Centrum voor tandheelkunde Geluwe, [name]

Anticipated number of study sites: 7 study sites, located in EU, US and CA

Anticipated number of subjects/implants: 200 subjects

Background and overall aim

The Astra Tech Implant System EV is the next step in the continuous evolution of the Astra Tech Implant System but the foundation for this new system is still the Astra Tech Implant System. The Astra Tech Implant System EV includes dental implants in diameters ranging from 3 mm up to 5.4 mm, and lengths from 6 mm up to 17 mm. It also includes an extensive abutment assortment; patient-specific abutments as well as a wide range of pre-fabricated abutments. Utilizing a site-specific, crown-down approach, these components are designed to help support all clinical situations and soft tissue sculpturing requirements for final restorations.

The rationale for this retrospective study is to generate clinical data that supports that the OsseoSpeed EV implant is a viable treatment option that gives reliable results in everyday clinical practice.

A retrospective design is chosen because this design provides information on the everyday clinical use of the whole EV assortment rather than the controlled approach required in a prospective clinical investigation.

Study objectives

Primary objective

The primary objective is to evaluate implant survival. Survival is defined as that the study implant(s) are in situ at time of the study visit.

Secondary objectives

The secondary objectives are to evaluate:

- Implant success

Implant in situ at time of the study visit and no ADEs related to the implant or adjacent peri-implant tissues reported from the day when the study implant(s) was installed until the end of the study.

- Prosthetic success

Implant, abutment, and restoration in situ at time of the study visit and no ADEs related to the reconstruction or adjacent peri-implant tissues reported from the day when the study position(s) was permanently included in a prosthetic restoration until the end of the study.

- Bone tissue response

Marginal Bone Levels (MBL) from radiographs.

- Soft tissue response

Probing Pocket depth (PPD) Bleeding on Probing (BoP) Presence of Plaque.

- Patient reported outcomes

Subjects rate 1) Chewing function, 2) Esthetics and 3) Satisfaction.

- Adverse Device Effects (ADE) and Serious Adverse Device Effects (SADE)

Adverse Device Effects related to implant, abutment, restoration, or adjacent peri-implant tissues reported from the day when the study implant(s) was installed until the end of the study.

Study design

This study is designed as a retrospective and multi-center study. The study population consist of subjects who received one or more OsseoSpeed EV implants during the period January 1st 2015 to December 31st 2016. Two hundred subjects will be enrolled, approximately 25-30 subjects per site. The study includes retrospective data collection from subjects' medical records and data collection from one prospective study visit with clinical examination.

The active study phase, at each study site, is estimated to 6 months and includes: contacting the subjects identified and randomized during the screening phase, recalling the subjects to the clinic to perform one study visit. During this visit the informed consent form (ICF) will be signed and the clinical examination will be performed.

The study starting date for each enrolled subject will be the date the ICF is signed, and the study ends when he/she finalize the prospective study visit.

Study population

The study population will include subjects that received OsseoSpeed EV implants during January 1st 2015 to December 31st 2016. At least 6 study sites will be needed to enroll the required number of subjects.

The study subjects will be recruited from the clinics' full population of individuals previously treated with OsseoSpeed EV implants, replacing one or more teeth, anywhere in the mouth as part of their prosthetic restorations. The implants evaluated in this study will all have been placed according to the standard practice for treatment with OsseoSpeed EV implants.

Inclusion criteria

For inclusion in the study subject must meet all of the following criteria:

1. Subject \geq 18 years at time of implant installation.
2. Subject signed and dated the informed consent form.
3. Having installed one or more OsseoSpeed EV implants between January 1st 2015 and December 31st 2016.

Exclusion criteria

Any of the following is regarded as a criterion for exclusion from the study:

1. Unlikely to be able to comply with study procedures, according to Investigators judgment.
2. Subject is not willing to participate in the study or not able to understand the content of the study.
3. Involvement in the planning and conduct of the study.
4. Simultaneous participation in another clinical study that may interfere with the present study.
5. Severe non-compliance to CIP as judged by the Investigator and/or Dentsply Sirona Implants.

Study products

The investigational product (OsseoSpeed EV implant) is already included in a restoration in the subject at enrollment, thus this study does not involve the installation of any investigational products.

Indication

Implant used for single, partial or full-prostheses.

Statistical methods

General

If nothing else is stated, descriptive statistics will be given for each variable in the study. This means number of subjects or study positions (n), mean, median, standard deviation (SD), minimum (min) and

maximum (max) values will be presented for continuous data and frequencies and percentages for categorical data.

In relation to objectives

The primary analysis of the study is to estimate the proportion of implants not failing (i.e., survive) over a fixed period of time. Each study position will be categorized as survived (Yes/No). Position will be categorized as survived = Yes, when the implant has been in situ during study. Position will be categorized as survived = No, when the implant has been lost during study. The proportion of survived study positions will be calculated by dividing the number of study positions with survived=Yes, by the total number of study positions. This proportion will be presented together with a 95% confidence interval (using the exact Binomial approach) independent of the follow-up time.

The primary analysis of the study is to estimate the proportion of implants/subjects not failing (i.e., survive).

The expected (i.e., the true) survival rate of the implants is denoted Π and is assumed to be 97 %. The null-hypothesis that the survival rate is less than 91% will be tested using the exact Binomial test, i.e. the following hypotheses will be tested:

$$H_0: \Pi < 91 \%$$

versus

$$H_1: \Pi \geq 91 \%$$

Survival will be calculated on a study position level although the sample size calculation provides the number of subjects needed; this approach is chosen since we do not in advance know the number of study positions per subject. Consequently, we assume that study positions within one subject are independent of each other if more than one.

Implant survival will be analyzed on an implant level (i.e., percent of survived implants) as well as on subject level (i.e., percentage of subjects with no lost implants) i.e., if one or more implant(s) fail within a subject the subject is considered as a failure.

Primary analysis will be done on implant level.

Study timetable

Anticipated First Site Initiated:	2019 January
Anticipated Last Site Initiated:	2019 February
Anticipated First Subject Enrolled:	2019 February
Anticipated Last Subject Last visit:	2019 August
Anticipated Data Base Lock:	2019 September

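### Success and ADE endpoints reach back years before consent, but for complications resolved before the visit the plan names only the clinic's records, so missed events count as success

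*Combined protocol and SAP*

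**What the plan says.** Under Study objectives, Secondary objectives, three outcomes depend on which adverse device effects have been reported:

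- **Implant success:** the implant must be in place when examined, with "no ADEs related to the implant or adjacent peri-implant tissues reported from the day when the study implant(s) was installed until the end of the" … (that is, until the visit is completed).
- **Prosthetic success:** the definition opens with "Implant, abutment, and restoration in situ at time of the study visit and no ADEs related to the reconstruction", extends to the adjacent tissues, and sets the ADE part as "reported from the day when the study position(s) was permanently included in a prosthetic restoration until the end of the study".
- **ADE and SADE:** effects related to implant, abutment, restoration or adjacent tissues, "reported from the day when the study implant(s) was installed until the end of the study".

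Study design names the data sources: "retrospective data collection from subjects' medical records and data collection from one prospective study visit with clinical examination". It also sets the subject's time in the study: "The study starting date for each enrolled subject will be the date the ICF is signed, and the study ends when" the visit is completed. Consent is signed at that same visit.

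The outcomes listed for evaluation are pocket depth, bleeding, plaque, bone levels from radiographs, and three patient ratings (chewing, appearance and satisfaction). No question about past complications or treatment elsewhere is listed. The document does not say how an ADE is to be recognised in routine notes, or how a position with an incomplete record is to be classified.

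**The concern.** Almost the whole ADE window lies before consent and before any study procedure. A loosened screw since tightened, an infection since treated or a crown since remade may leave nothing to see at the visit. A remade restoration is itself in place and can meet that part of prosthetic success. If the event is also missing from the clinic's notes, nothing the plan describes would bring it to light, and the position meets the success definition.

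The error runs mainly one way: missed events raise both success rates and lower the ADE rate. That is also the direction of the stated rationale, which is to produce data supporting the implant as a reliable option in everyday use. Nor does a larger sample help, because the confidence interval narrows around a shifted value.

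**Working it through.** **1. Length of the window.** The inputs are the installation period in the inclusion criteria (1 January 2015 to 31 December 2016) and the Study timetable (first subject February 2019, last visit August 2019). The plan states no follow-up length to reproduce.

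- Shortest: 31 December 2016 to 1 February 2019 = 762 days; 762 / 365.25 = 2.09 years.
- Longest: 1 January 2015 to 31 August 2019 = 1,703 days; 1,703 / 365.25 = 4.66 years.

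This 2.1 to 4.7 years applies to implant success and to the ADE objective. The prosthetic window opens at permanent restoration, and the lag from installation is not given. With an assumed lag of 2 to 6 months, the shortest window is 1.6 to 1.9 years and the longest 4.2 to 4.5 years.

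**2. Which failures can be missed.**

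| Event before the visit | Visible from a source the plan names? |
|---|---|
| Implant lost | Yes, by the in-situ check |
| Abutment or restoration missing at the visit | Yes, by the in-situ check for prosthetic success |
| Complication still present | Can be seen at examination or on radiographs |
| Resolved, recorded at the clinic | Yes, from the records |
| Resolved, unrecorded or treated elsewhere | No named source, unless it left a visible trace |

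Only the last row is exposed.

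**3. Size, as an illustration for implant success.** Let T be true success, L the share of implants lost, and u the share of the remaining failures missed by both records and examination. Losses cannot be missed, so

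reported success = T + (1 − T − L) × u.

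L = 1 − 0.97 = 0.03, from the survival rate assumed under Statistical methods. T and u are assumptions; the documents give neither.

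| T | 1 − T − L | u = 10% | u = 30% | u = 50% |
|---|---|---|---|---|
| 90% | 7% | 90.7% | 92.1% | 93.5% |
| 80% | 17% | 81.7% | 85.1% | 88.5% |

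At T = 90%, the share of positions with the implant in place but a related ADE is 7% in truth. It would be reported as 7% × 0.9 = 6.3% down to 7% × 0.5 = 3.5%.

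No such split can be made for prosthetic success, because the plan gives no expected rate of abutment or restoration loss.

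**The case against.** The strongest reply is that this is a gap in the description and that no miscounting has been shown. The text does not forbid taking a history. An earlier event that a subject mentions at the visit would be reported before the end of the study and so fits the present wording. The exclusion criteria refer to a CIP, and ADE procedures may be set out there. Past bone loss can remain visible on radiographs, and a site may notice that a restoration is not the one in its notes. The endpoints are secondary and descriptive, with no hypothesis test. Incomplete records are a familiar limit of a retrospective design, which the sponsor chose openly.

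Much of this stands, and it rules out several stronger readings that a reader might infer:

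- That success requires nothing more than the absence of a reported ADE. Both definitions also require the components in situ.
- That records are the only possible source, or that no ADE reporting existed in 2015 to 2018. The documents say neither.
- That every failure could go unseen. Applying u to all failures would give 0.90 + 0.10 × 0.5 = 95% at T = 90%; with losses seen at the visit it is 93.5%.
- That sites with fuller notes would fare worse in a planned comparison. No between-site comparison is described.

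What the reply does not remove is that events volunteered by chance are not systematic ascertainment. Three objectives rest on past events for which the plan describes no active enquiry.

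**Conclusion.** The point holds in a limited form. For complications that resolved before the visit and were unrecorded or treated elsewhere, the plan names no source that would find them. Such positions would be scored as successes, so implant and prosthetic success are biased upward and ADE rates downward.

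The size cannot be estimated from the documents. With the plan's 97% survival, an assumed true implant success of 90% and 10% to 50% of the other failures missed, the overstatement is 0.7 to 3.5 percentage points. At an assumed true success of 80% it is 1.7 to 8.5 points. These figures show scale only.

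A reader might carry the concern over to the primary result. The documents do not support that: under the primary objective, survival is in-situ status at the visit and does not use ADE reports.

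**What to change.** - **Add one fixed CRF history question at the existing visit:** since installation, has any study implant, abutment or restoration had a problem, repair, remake or treatment, at this clinic or elsewhere, and when?
- **Have the investigator assess each yes for device relatedness,** without requiring a matching record entry. Requiring one would fail in exactly the cases at issue.
- **Reword the success definitions** to *no related ADE in the medical record, by subject history or at examination*, each over its present window, and use the same three sources for the ADE/SADE objective.
- **Report ADE counts by source** (record, history, examination), so that a reader can see how much the records alone would have missed.

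The date of the last clinic contact before the visit may be recorded as optional, descriptive information. Success split by whether a follow-up contact is on record should not be presented as a less biased estimate, because subjects with contacts may over-represent those who came back with complaints.

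The cost is one question and one descriptive table, with no added visits or subjects. The downside is some recall error and success rates that may be slightly less favourable.

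### The Study products text describes the implant as already restored at enrollment, the same visit at which survival is scored; this conflicts with the installation-only inclusion criterion and could lead sites to omit early failures

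*Combined protocol and SAP*

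**What the plan says.** All places are in the combined protocol and SAP.

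- **Study products:** "The investigational product (OsseoSpeed EV implant) is already included in a restoration in the subject at enrollment". The rest of that sentence draws the consequence that the study installs no devices.
- **Study population:** each clinic's entire pool of such patients is the source, described as "individuals previously treated with OsseoSpeed EV implants, replacing one or more teeth, anywhere in the mouth as part of their prosthetic restorations".
- **Inclusion criteria, item 3:** "Having installed one or more OsseoSpeed EV implants between January 1st 2015 and December 31st 2016". Neither the inclusion nor the exclusion list mentions restoration or in-situ status.
- **Primary objective:** "Survival is defined as that the study implant(s) are in situ at time of the study visit".
- **Study design:** on the one visit, "During this visit the informed consent form (ICF) will be signed and the clinical examination will be performed". Each subject's study period begins at consent and ends when that visit is completed.
- **Statistical methods:** "Position will be categorized as survived = No, when the implant has been lost during study". The denominator is the total number of study positions. The assumed survival is 97% and the exact binomial test is against 91%.
- **Secondary objectives:** implant success and adverse device effects count from the day of installation. Prosthetic success has its own, later start, when the position is permanently restored.

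**The concern.** The plan gives two descriptions of who is studied. The inclusion criterion is based on installation. The Study products sentence describes subjects whose implant is in a restoration on the day they enroll, which is the day survival is scored.

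A subject whose only study implant was lost before it was restored meets the criterion but does not fit the description. The same holds for a subject whose only implant was restored and later lost. The Study population wording can also be read as referring to restored cases. A site compiling its candidate list could adopt that reading in good faith.

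The omitted subjects would be failures for both survival and implant success, so both would be biased upward. The loss would occur before random selection, so no analysis of the enrolled sample could recover it. It would affect the primary endpoint and the plan's only hypothesis test.

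**Working it through.** **1. The passages side by side**

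| Subject's only implant | Meets inclusion criterion 3? | Fits the Study products description? | In situ at the visit? |
|---|---|---|---|
| Lost before restoration | Yes | No | No |
| Restored, later lost | Yes | No, if read as restored on the day of enrollment | No |
| Restored and present | Yes | Yes | Yes |

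Only the third row fits the description read literally, and it contains no failures. No section says that implants lost before restoration stay in the denominator as failures.

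**2. The failure definition**

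The Statistical methods section scores a position as a failure if the implant was lost during the study, but the study runs from consent to the end of one visit. Taken literally, an implant lost before consent was neither in situ during the study nor lost during it, so it falls in neither category. This wording needs correcting along with the eligibility text.

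**3. Size of the possible effect**

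From the documents: 200 subjects, null rate 91%, assumed rate 97%, exact binomial test.

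Assumptions, because the documents do not give these: one position per subject (n = 200), one-sided 2.5% level, a share f of all losses occurring before restoration, and all of those losses unlisted.

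*Rule without selection.* The smallest count x with P(X ≥ x | 200, 0.91) ≤ 0.025 is 191. The actual level is 0.0121, and P(X ≥ 191) at 0.97 is 0.919. The plan's 200 cannot be reproduced, because no alpha, sidedness, power or dropout is stated. The point does not depend on it.

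*Effect of selection.* With true survival S from installation, survival among listed positions is

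S_listed = S / [1 − f(1 − S)].

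For S = 0.91 and f = 0.25: 0.91 / (1 − 0.25 × 0.09) = 0.91 / 0.9775 = 0.931.

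| f | Implants lost before restoration, f × 9% | Listed survival at true 91% | P(X ≥ 191) |
|---|---|---|---|
| 0 | 0 | 91.0% | 1.2% |
| 10% | 0.9% | 91.8% | 3.1% |
| 25% | 2.25% | 93.1% | 11% |
| 50% | 4.5% | 95.3% | 53% |

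As the hypotheses are written, 91% itself lies in the alternative. The table therefore gives the limit as true survival approaches 91% from below. Inside the null, at a true 90% with f = 50%, listed survival is 0.90 / 0.95 = 94.7% and the chance of passing is 39%.

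*If the level is one-sided 5%.* The rule becomes 189 or more (actual level 4.7%). At a true 91% and f = 25%, the chance of passing is 27%.

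*If only half of the early losses are missed.* Suppose 1% to 5% of implants are lost before restoration and half of these are unlisted. A true 91% then appears as 0.91 / 0.995 = 91.5% to 0.91 / 0.975 = 93.3%. The chance of passing is 2.1% to 13.6% at the 2.5% rule.

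*At the assumed 97%.* Listed survival is 0.97 / 0.9925 = 97.7% at f = 25% and 0.97 / 0.985 = 98.5% at f = 50%. The estimate rises by 0.7 or 1.5 points. The test already passes about 92% of the time without selection, and passing is the correct answer.

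**The case against.** The strongest defense is that the Study products sentence explains why no device is supplied and does not set entry conditions. It stands outside the eligibility lists. The Study design and Study population sections both define subjects by having received an implant in the window. Recruitment is from the full treated population, and the phrase about prosthetic restorations can describe the purpose of treatment. All of this is fair, and it means that the plan contains no rule excluding early losses.

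A reader might infer that survival is 100% by construction, since an implant in a restoration at the visit must be in situ. The documents do not support that as the intended design. They provide a category for implants that did not survive, assume 97% rather than 100%, define subject-level failure, collect medical records, and treat presence of the restoration at the visit as an outcome. A reader might likewise infer that sites will list only restored cases. No section says so; how candidates are listed before randomization is not described.

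The figures above also sit toward the unfavorable end. They assume that every early loss is missed and that each subject has one implant. The plan expects some subjects to have several, and a subject with one lost and one restored implant could still be listed.

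What remains is that the Study products sentence is an unqualified statement about every subject that the formal criteria contradict, and nothing in the plan tells a site which governs. Record review and multiple implants do not recover a subject with a single lost implant who was never listed.

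**Conclusion.** The passages conflict and should be reconciled. The omission of early failures is a possibility that the wording leaves open; it is not a stated rule, and it is not shown to occur. The direction, if it does occur, is clear: survival and implant success are overstated.

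The size is unknown because the documents do not give the share of losses that precede restoration. Under the stated assumptions, the chance of passing at a true 91% goes from 1.2% to 3%, 11% or 53% for shares of 10%, 25% or 50%. It is smaller with partial omission or several implants per subject. Leaving out subjects whose implants were lost after restoration would add to it. If true survival is near the assumed 97%, the estimate would be somewhat too high but the conclusion against 91% would rarely change. Severity: should be fixed.

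**What to change.** 1. **Study products:** say that the implant was installed before enrollment, and that eligibility does not depend on whether it was restored or is still in situ.
2. **Study population:** define the source as everyone in whom an OsseoSpeed EV implant was installed in the 2015-2016 window, whether or not it was later restored.
3. **Listing:** require each site to build its candidate list from installation (surgical) records before random selection.
4. **Denominator:** state that every study implant installed in the window counts.
5. **Failure definition:** in Statistical methods, replace the reference to loss during the study with *lost at any time from installation to the study visit*, and align the definition of survived = Yes with it. Without this, a loss before consent would still not literally be scored as a failure.

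The cost is a few sentences of protocol text, a little more listing work at each site, and possibly a slightly lower reported survival rate. No visits or subjects are added.

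### The primary endpoint does not tie a study position to one implant, so an implant lost before the visit and replaced in 2015-2016 can be scored as survived

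*Combined protocol and SAP*

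**What the plan says.** Four parts of the document bear on how a position is scored.

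- **Primary objective.** "Survival is defined as that the study implant(s) are in situ at time of the study visit".
- **Statistical methods, In relation to objectives.** The target is set out as: "The primary analysis of the study is to estimate the proportion of implants not failing (i.e., survive) over a fixed period of time". The scoring follows: "Position will be categorized as survived = Yes, when the implant has been in situ during study", and "Position will be categorized as survived = No, when the implant has been lost during study". The ratio is then defined: "The proportion of survived study positions will be calculated by dividing the number of study positions with survived=Yes, by the total number of study positions". Further on, the plan adds: "Primary analysis will be done on implant level". A subject-level analysis counts a subject as a failure if any implant was lost.
- **Study design.** The study period for a subject is defined: "The study starting date for each enrolled subject will be the date the ICF is signed, and the study ends when he/she finalize the prospective" visit. On consent it says: "During this visit the informed consent form (ICF) will be signed and the clinical examination will be performed".
- **Inclusion criteria and Study products.** Criterion 3 admits subjects with one or more OsseoSpeed EV implants placed from the start of 2015 to the end of 2016. It does not restrict this to the first implant at a site. Study products describes the investigational implant as already carrying a restoration when the subject enrols.

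The document does not define a study position or a study implant, and it does not mention replacement of a lost implant.

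**The concern.** The quantity of interest is the proportion of implants that do not fail, but the unit counted is the position. The two agree only if each position has held a single implant. Once a lost implant has been replaced, someone must decide which implant the position refers to, and the plan gives no rule.

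The failure rule does not settle the matter, because it is limited to losses during the study. As the plan defines it, each subject's study lasts for one visit in 2019, so a loss in 2015 lies outside it.

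Misclassification by this route can only favour the device: a failure may be read as a survival, never the reverse. With seven sites planned and no written rule, two sites could also score the same history differently.

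**Working it through.** **1. The wording applied to one history.** Take an invented case. An OsseoSpeed EV implant is placed in March 2015, lost in June 2015, and replaced at the same site by another OsseoSpeed EV in November 2015. The replacement is in place at the 2019 visit.

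- *Is the position a No?* The rule needs a loss during the study. The study runs from consent to the end of the same visit, and the loss came years earlier. Literally, it is not a No.
- *Is it a Yes?* The replacement was placed within the window and carries a restoration at enrolment, so it can be taken as the position's implant. It was in place throughout the visit. Literally, it can be a Yes.
- *Plain intent.* The primary objective asks about the study implants themselves, and the implant-level analysis is a percentage of implants that survive. On that reading the first implant failed.
- *Subject level.* The criterion of no lost implants, taken plainly, makes this subject a failure while the position counts as survived. If a site registers only the replacement, the subject may count as a success too.

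A related gap concerns an implant lost before the visit and not replaced. It fits neither the Yes nor the No wording in Statistical methods, although the primary objective makes it a failure.

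**2. The plan's own figure.** The plan gives 200 subjects, a null survival of 91% and an assumed true survival of 97%, tested by an exact binomial test. It gives no significance level, sidedness, power or dropout, so 200 can be checked for plausibility but not reproduced. With one position per subject and independence, the upper tail is P(X ≥ k) = Σ C(200, j) p^j (1 − p)^(200 − j), summed over j = k to 200.

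- One-sided 2.5% (assumed): at p = 0.91, P(X ≥ 190) = 0.0251 and P(X ≥ 191) = 0.0121. So 191 survivors are needed, which is at most 9 losses. Power at 97% is 91.9%.
- One-sided 5% (assumed): 189 survivors are needed, which is at most 11 losses (actual level 0.0472). Power at 97% is 98.2%.

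**3. Rescoring replaced losses.** Suppose 12 of 200 index implants were lost (an assumption).

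| Losses scored as survived | Result | Exact 95% CI | One-sided p |
|---|---|---|---|
| 0 of 12 | 188/200 = 94.0% | 89.8 to 96.9% | 0.082 |
| 3 of 12 | 191/200 = 95.5% | 91.6 to 97.9% | 0.012 |
| 6 of 12 | 194/200 = 97.0% | 93.6 to 98.9% | 0.0007 |

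Three rescored losses change the test result at one-sided 2.5%. At one-sided 5% a single one would do so, because 12 losses fail and 11 pass.

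**4. General form.** Let s be the share of losses that are replaced, still in place at the visit, and scored Yes. Observed survival is p + (1 − p)s.

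| s (assumed) | True 97% reads as | True 91% reads as | Chance of passing at true 91%, one-sided 2.5% |
|---|---|---|---|
| 0 | 97.0% | 91.0% | 1.2% |
| 25% | 97.75% | 93.25% | 12.7% |
| 50% | 98.5% | 95.5% | 58.7% |
| 75% | 99.25% | 97.75% | 98.4% |

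At the planned 97%, about 200 × 0.03 = 6 losses are expected. Then 194/200 passes without any rescoring (p = 0.0007), so the effect is on the estimate and not on the test.

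**The case against.** The strongest reply is that the text does not ask whether just any implant is in place. The primary objective refers to the study implants, the Yes and No rules refer to a particular implant, and the primary analysis is stated to be at implant level. On a plain reading, a lost study implant is a failure whatever later occupies the site. The ratio sentence alone does not produce the problem. All of this stands, and it limits the claim to what the wording allows.

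A reader might infer more: that the rule turns every replaced failure into a success, including replacements placed in 2017 or later. The document does not support that. Study implants are those placed in 2015-2016, so a later one is not a study implant and cannot meet the primary objective's definition.

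A reader might also take the larger percentages in the last table as expected error rates. They require true survival at the null value together with a replacement share of half or more, and the document gives no replacement share at all.

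The reply also notes that counting both implants, one failed and one survived, would fit an implant-level analysis. That is a coherent alternative, but the plan does not state it either.

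The reply does not remove the conflict over time. The failure rule is confined to a study period that begins and ends at one visit, while the study is retrospective. An implant placed in the window as a replacement meets the plan's description of a study product. The plain reading therefore has to be supplied by the reader against the literal text.

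**Conclusion.** The concern holds in limited form. The scoring rule is wrong as written: followed literally, a position whose implant was lost before the visit and replaced by another OsseoSpeed EV in 2015-2016 can be scored as survived, although the evident intent is that it failed. Any resulting error favours the device.

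The size is illustrative only. It rests on 200 independent positions, a one-sided 2.5% level and assumed replacement shares, none of which the document states. Under those assumptions, rescoring 3 of 12 losses is enough to move the result from not passing to passing. If true survival is near 97%, the test result would probably be unaffected and the estimate would be raised by 0.75 to 2.25 percentage points for shares of 25% to 75%.

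This should be corrected before data are collected, because choosing the index implant once outcomes are known would itself be open to bias. It does not undermine the design.

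**What to change.** Amend the definitions in Statistical methods and use them throughout.

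1. Define each study position by the first OsseoSpeed EV implant installed there in the 2015-2016 window, identified from the medical record.
2. Replace the reference to loss during the study with loss from installation to the study visit. The implant-success and adverse device effect definitions already start at installation.
3. Score survived = No if that index implant was lost or removed in that period, whether or not it was replaced.
4. Keep replacements out of the primary numerator and denominator, and list them separately. If the sponsor prefers to count both implants, the plan should say so and count the first as failed.
5. Use the same index implant for the subject-level and implant-success analyses.

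The cost is a short definition and a check for replacements in records that the sites already review. Reported survival may be slightly lower.
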